5.3.3. Part C Study Drug Dosing, Study Progression, and Dose Escalation

Overview: Part C is optional and may be conducted if VIR-3434 is found to have an acceptable safety and tolerability profile in HBeAg-negative subjects with HBsAg levels < 3,000 IU/mL in Part B. For cohorts in Part C, HBeAg-negative and HBeAg-positive subjects with HBsAg \geq 3,000 IU/mL will be enrolled.

There are 3 optional cohorts in Part C each evaluating up to 900 mg SC (Table 5). Cohort 1c will be the first cohort to initiate enrollment. Doses explored in Part C cohorts will not exceed the highest dose level in Part B that was determined to be safe by the SRC. Part C cohorts may be enrolled in parallel.

Initiation of Part C: Cohort 1c may be initiated after SRC review of available data for all subjects in Part A and Part B through the Week 4 visit for the cohort of subjects in Part B who are receiving a matching or higher dose.

Table 5: Part C Cohort Overview

Study Part	Cohort	Route	Dose Level	Active:Placebo
C	1c (optional)	SC	up to 900 mg	6:2
C	2c (optional)	SC	up to 900 mg	6:2
C	3c (optional)	SC	up to 900 mg	6:2

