6.4. Parts B, C, and D Inclusion Criteria

Each subject must meet all the following inclusion criteria at screening to be eligible for enrollment in the study:

1. Age 18 (or age of legal consent, whichever is older) to 65 years
2. Weight ≥ 40 kg to ≤ 125 kg
3. Chronic HBV infection as defined by the following criteria:
Positive serum HBsAg, HBV DNA, or HBeAg on 2 occasions at least 6 months apart based on previous or current laboratory documentation (any combination of these tests performed 6 months apart is acceptable)
4. Parts B and C only: On NRTI therapy for at least 2 months at the time of screening

5. Parts B and C only: HBV DNA < 100 IU/mL at screening
6. Part D only: HBV DNA \geq 1,000 IU/mL at screening
7. HBsAg > the lower limit of detection
8. Part B only: HBsAg < 3,000 IU/mL at screening
9. Part C only: HBsAg \geq 3,000 IU/mL at screening
10. Part B only: HBeAg-negative at screening
11. Negative anti-HBs at screening
12. Besides chronic infection with HBV, must be in good health, determined from medical history (e.g. chronic conditions such as hypertension, hyperlipidemia, gastroesophageal reflux disease, asthma, anxiety and depression must be well controlled), and no clinically significant findings from physical examination, 12-lead ECG, vital signs, and laboratory values.
13. Female subjects must have a negative pregnancy test or confirmation of postmenopausal status. Post-menopausal status is defined as 12 months with no menses without an alternative medical cause. WOCBP must have a negative blood pregnancy test at screening and a negative urine pregnancy test on Day 1, cannot be breast feeding, and must be willing to use highly effective methods of contraception (Section 6.6) 14 days before study drug administration through 40 weeks after study drug administration. Female subjects must also agree to refrain from egg donation and in vitro fertilization from the time of study drug administration through 40 weeks after study drug administration.

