8.17. Assessment of Screening Viral Parameters, Antiviral Activity, and Resistance Surveillance

During Parts B, C, and D, assessment of screening viral parameters will include: HBsAg, anti-HBs, HBeAg (qualitative), and HBV DNA.

Assessments of antiviral activity performed after screening will include: HBsAg, anti-HBs, HBeAg (qualitative; should only be collected for Parts C and D subjects who are HBeAg qualitative positive at screening), HBeAg (quantitative; should only be collected for Parts C and D subjects who are HBeAg qualitative positive at screening), anti-HBe, HBV RNA, hepatitis B core-related antigen (HBcrAg), and HBV DNA.

Resistance surveillance to monitor for the potential development of resistance to NRTIs or VIR-3434 will be conducted for all subjects who receive study drug. HBV genome sequencing will be attempted in subjects with confirmed HBV DNA breakthrough as defined by having either HBV DNA $\geq 1 \log_{10}$ IU/mL above nadir for 2 consecutive visits or ≥ 500 IU/mL measured at 2 consecutive study visits after having been < 500 IU/mL. HBV genome sequencing will also be attempted in subjects who discontinue early from the study with HBV DNA ≥ 500 IU/mL. As it will not be known at the time of visit if a subject has virologic breakthrough, samples for resistance surveillance will be collected at all study visits noted in the SOA. Samples collected for resistance surveillance may be used to perform additional viral analyses, including viral sequencing.

Details regarding the processing and shipping of the samples are provided in the Laboratory Manual.

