Urinalysis ^{n,o}	X	X			X		X							
Urine for drugs of abuse ^p	X													
Study drug administration ^q		X												
Blood samples for PK analysis ^r		X	X	X	X	X	X	X	X	X	X	X	X	X
Blood samples for immunogenicity analysis ^s		X					X	X	X	X	X	X	X	X
Blood sample for quantitative HBsAg	X	X	X	X	X	X	X	X	X	X	X	X	X	X
Blood sample for anti-HBs	X				X		X	X	X	X	X	X	X	X
Blood sample for HBeAg qualitative	X								X ^t					X ^t
Blood sample for HBeAg quantitative ^t		X						X	X					X
Blood sample for anti-HBe		X							X					X
Blood sample for HBV RNA quantitation and HBcrAg quantitation		X						X	X	X		X	X	X

Part B, C, and D															
Study Stage	Screening	Dosing Day ^a	Post-dose Follow-up Period							Extended Follow-up Period ^b					
Study Visit Week					W1		W2	W4	W8/ET ^c	W12	W16	W24	W32	W40 / EF ^d	
Study Visit Day±Visit Window	D -42 to -1	D1 ^e	D2	D4+1	D8±1	D11±1	D15±2	D29±2	D57±7	D85 ±7	D113 ±7	D169 ±7	D225 ±7	D281 ±7	
Blood sample for HBV DNA quantitation ^u	X	X	X ^v	X ^v	X	X ^v	X	X	X	X	X ^v	X	X ^v	X	
Blood sample for analysis of peripheral immune responses ^w		X			X		X	X	X	X		X		X	
Blood sample for RNA Paxgene tube ^x		X			X		X	X	X	X		X		X	
HBV resistance surveillance ^{u,y}		X			X		X	X	X	X	X	X	X	X	
Blood sample for Fc gamma receptor genotyping and for immunoglobulin allotyping		X													
CCI															
Local tolerability ^{aa}		X	X	X	X										
Review/record AEs ^{bb}	X									X					
Concomitant medications								X							
NRTI medication adherence ^{cc}								X							

AE = adverse event; ECG = electrocardiogram; EF = end of follow-up; ET = end of treatment; HBcrAg = hepatitis B core-related antigen; HBeAg = hepatitis B e-antigen; HBsAg = hepatitis B surface antigen; HBV = Hepatitis B Virus; NRTI = nucleoside/nucleotide reverse transcriptase inhibitor; PK = pharmacokinetic; SAD = single ascending dose

Note: When scheduled at the same timepoints, the assessments of vital signs and 12-lead ECGs must be performed before the blood sample collections.

- ^a Subjects may be admitted to the clinical investigative site on Day -1 or 1 and discharged after all study assessments are performed on Day 1. Patients must be monitored through at least 6 hours post-dose prior to discharge.

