6.7. Antiviral Activity Analysis

All antiviral activity analyses described in this section will be based on the FAS and applied for Part B, C, and D only, unless specified otherwise.

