6.7.1. Definition of Variables

Selected antiviral activities will be analyzed through the following variables:

- HBV viral parameters (quantitative): HBsAg, HBV RNA, HBcrAg, and HBV DNA (Part D only)
- HBeAg loss: HBeAg changing from positive at baseline to negative at any post-baseline visit (up to Week 8), which will be only applied for participants from Part C and D with qualitative positive HBeAg at baseline.
- HBsAg loss: HBsAg changing from positive (\geq LLOQ) at baseline to negative ($<$ LLOQ) at 2 separate, consecutive, post-baseline visits during the follow-up period (up to Week 8) with at least 2 weeks apart
- Anti-HBs seroconversion: HBsAb changing from negative or missing at baseline to positive (\geq LLOQ) at any post-baseline visit (up to Week 8), which will be only applied for participants with negative or missing Anti-HBs at baseline.

- Anti-HBe seroconversion: HBeAb changing from negative or missing at baseline to positive at any post-baseline visit (up to Week 8), which will be only applied for participants with negative or missing Anti-HBe at baseline.

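### Anti-HBe seroconversion in SAP 6.7.1 is defined by antibody alone, so it counts changes that are not e-antigen seroconversion and cannot be read against HBeAg loss

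*SAP*

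**What the plan says.** SAP 6.7 sets the scope: "All antiviral activity analyses described in this section will be based on the FAS and applied for Part B, C, and D only". Within it, SAP 6.7.1 gives two e-system variables.

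- **HBeAg loss** is a change from positive to negative, "which will be only applied for participants from Part C and D with qualitative positive HBeAg at baseline".
- **Anti-HBe seroconversion** is "HBeAb changing from negative or missing at baseline to positive at any post-baseline visit (up to Week 8". The definition sets one eligibility limit, on baseline antibody status and not on HBeAg or study Part: "which will be only applied for participants with negative or missing Anti-HBe at baseline".

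SAP 6.7.2 reports both, with HBsAg loss and anti-HBs seroconversion, as the number and percentage of participants who ever met the definition up to Week 8, by treatment cohort and placebo.

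On the populations, Protocol 6.4 has "Part B only: HBeAg-negative at screening". Protocol 5.3.3 says of Part C: "For cohorts in Part C, HBeAg-negative and HBeAg-positive subjects" are enrolled; Protocol 5.1.4 admits both groups to Part D as well. After screening, Protocol 8.17 limits the antigen test: "HBeAg (qualitative; should only be collected for Parts C and D subjects who are HBeAg qualitative positive at screening". The row "Blood sample for anti-HBe" in the Parts B, C and D schedule (Protocol Appendix 3) carries no such limit and has samples on Day 1, Week 8 and Week 40.

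**The concern.** The SAP recognises that HBeAg loss needs HBeAg at baseline, but sets no HBeAg condition on the antibody variable reported beside it. Four things follow.

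- (a) An HBeAg-negative subject whose anti-HBe turns positive is counted, with no HBeAg to convert from. This covers everyone in Part B and any HBeAg-negative subject in Parts C and D.
- (b) A Part C or D subject who gains anti-HBe while HBeAg stays positive is counted.
- (c) A subject with no baseline anti-HBe result who is positive at Week 8 is counted, although no change was observed.
- (d) In Parts C and D each cohort percentage mixes HBeAg-positive and HBeAg-negative subjects, so it has a different population from HBeAg loss.

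At stake is how the row is read. Someone comparing seroconversion with HBeAg loss in the same cohort would be comparing different subjects and, in part, different events.

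**Working it through.** The plan gives no figure to reproduce here: SAP 3.2 has no sample size calculation and SAP 4 has no hypotheses. The check is to list every result pattern that meets the SAP rule and ask which of them are e-antigen seroconversion.

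**Rules compared**

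- SAP rule (6.7.1): baseline anti-HBe negative or missing, and anti-HBe positive after baseline.
- HBeAg-tied rule: baseline HBeAg positive and anti-HBe observed negative, then HBeAg negative and anti-HBe positive.

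**Enumeration.** With post-baseline anti-HBe fixed at positive, the SAP rule admits 2 baseline anti-HBe states × 2 baseline HBeAg states × 2 post-baseline HBeAg states = 8 patterns.

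| Baseline anti-HBe | Baseline HBeAg | Post-baseline HBeAg | SAP rule | Tied rule |
|---|---|---|---|---|
| negative | negative | negative | counted | no |
| negative | negative | positive | counted | no |
| negative | positive | negative | counted | **yes** |
| negative | positive | positive | counted | no |
| missing | negative | negative | counted | no |
| missing | negative | positive | counted | no |
| missing | positive | negative | counted | no |
| missing | positive | positive | counted | no |

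Grouped without overlap: 4 patterns start HBeAg-negative (a), 2 stay HBeAg-positive (b), 1 loses HBeAg but has no baseline antibody result (c), and 1 meets the tied rule; 4 + 2 + 1 + 1 = 8. Missing baseline anti-HBe appears in 4 of the 8, across these groups. These are logical patterns, not frequencies, so 7 of 8 is not an error rate. Within a baseline HBeAg-negative subject the two post-baseline HBeAg states cannot be told apart, because HBeAg is not collected after screening in that group.

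**Effect on denominators.** Under the tied rule the Part B denominator is 0. In a Part C or D cohort with 6 active subjects (6:2 allocation, Protocol Tables 5 and 6) it is between 0 and 6. The documents do not give the HBeAg and anti-HBe mix that would narrow this.

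**Can the tied rule be derived?** Protocol Appendix 3 schedules anti-HBe at Week 8 for Parts B, C and D, and qualitative HBeAg at Week 8 for Part C and D subjects who were HBeAg-positive at screening. Both results therefore exist at the same visit in the group the rule needs. In Part B the rule neither applies nor could be checked.

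**The case against.** The strongest reply is that the SAP says anti-HBe seroconversion, not HBeAg seroconversion, and that the literal meaning is appearance of antibody. The neighbouring anti-HBs variable has the same antibody-only form, with no requirement that HBsAg be lost. Protocol 10.6 also lists anti-HBe among the data to be summarised for Parts B, C and D, so showing it in Part B follows the protocol.

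Much of this stands. The literal reading is possible, and anti-HBe should still be summarised in Part B. The parallel with anti-HBs is incomplete, though. Protocol 6.4 requires every Part B, C and D subject to have detectable HBsAg and negative anti-HBs at screening (criteria 7 and 11), so eligibility supplies the at-risk population for the s system. No criterion does so for HBeAg and anti-HBe across the three Parts. The literal reading also leaves (c) and (d) untouched: a missing baseline is still treated as negative, and the Part C and D percentages still mix the two HBeAg groups.

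It is also fair that little depends on the row. SAP 4 calls the study exploratory, anti-HBe is not among the readable primary or secondary endpoints, and SAP 6.1 provides individual listings in which antibody and HBeAg can be compared where both were measured. The exploratory endpoints are redacted, so an HBeAg-based definition there cannot be ruled out.

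**Conclusion.** The point holds as a minor defect of definition. As written, the row counts (a), (b) and (c), and in Parts C and D it cannot be read against HBeAg loss (d). Its numerical size cannot be computed, because the documents do not give baseline anti-HBe status.

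Three stronger readings are tempting and are not supported.

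- A reader might infer that all Part B subjects, or all subjects who remain HBeAg-positive, are counted as seroconverters. Only those who are positive after a negative or missing baseline are counted; a subject anti-HBe-positive at baseline is excluded.
- A reader might take the Part B share as the extent of the problem. SAP Table 2 shows 4 Part B, 3 Part C and 2 Part D cohorts enrolled; at about 8 each this is 32 + 24 + 16 = 72, and 32/72 = 44%. But SAP 6.7.2 reports by cohort and placebo, and the protocol synopsis combines placebo within each Part. Part B counts therefore do not enter the Part C or D rates, and no planned summary uses that share.
- A reader might quote what one count does to a cohort percentage. With 6 active subjects, of whom between 1 and 6 are eligible (an assumption, as the number is not given), one count is anything from 1/6 = 17% to 1/1 = 100%. That range reflects small cohorts and says nothing about how often a count would be misplaced.

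The conclusion rests on the readable text of SAP 6.7.1 being the definition that is programmed.

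**What to change.** In SAP 6.7.1, define e-antigen seroconversion only for Part C and D participants who are HBeAg-positive and anti-HBe-negative (observed, not missing) at baseline. Require HBeAg negative and anti-HBe positive at the same visit, which up to Week 8 means the Week 8 samples.

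Report any other change from an observed negative anti-HBe to positive in a separate row named 'anti-HBe newly positive', split by baseline HBeAg status. Part B appears there. Subjects without a baseline anti-HBe result enter neither row and stay in the listings.

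The cost is a change of SAP wording and a small amount of derivation and table programming before database lock, with no new samples. The downside is a smaller denominator for seroconversion in Parts C and D, possibly zero in some cohorts, and no Part B entry in that row. Renaming the existing variable alone would be cheaper, but would leave the missing-baseline rule and the mixed denominator in place.

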6.7.2. Analysis Methods

HBV viral parameters (quantitative), the raw values and the absolute change from baseline at each post-baseline visit up to Week 8 visit will be summarized descriptively (n, mean, SD, median, Q1, Q3, min, max) by VIR-3434 treatment cohort and placebo.

Similarly, the raw values and the change from baseline at nadir during the follow-up period up to Week 8 in HBsAg and HBV DNA (Part D only) will be summarized descriptively (n, mean, SD, median, Q1, Q3, min, max) by VIR-3434 treatment cohort and placebo.

In addition, mean (\pm SD) of change from baseline in HBsAg (Part B, C, and D) and HBV DNA (Part D only) will be plotted at each post-baseline visit up to Week 8 by VIR-3434 treatment cohort and placebo.

HBeAg loss, HBsAg loss, Anti-HBs seroconversion, and Anti-HBe seroconversion: the percentage and number of participants who ever met each of the variables during the follow-up period up to Week 8 will be summarized and presented by VIR-3434 treatment cohort and placebo.

6.8. Modifications

6.8.1. Modifications to the Approved Study protocol

Change and Rationale	Affected Sections
Team decided to use the All-Randomized Set for disposition data summary to cover other analysis sets in this summary table	Section 6.2.1
Team decided to change the name of “Antiviral Analysis Set” to “Full Analysis Set (FAS)” to be consistent with the industry convention. The FAS will be also used in summary of demographics and baseline characteristics as well as analysis of antiviral activities	Section 6.2 and Section 6.7
Team decided to change the PK Analysis Set by including all participants in the FAS with at least 1 measurable postdose concentration data to provide interpretable results	Section 6.5
Team decided to change the Immunogenicity Analysis Set by including all participants in the FAS who had at least 1 sample that has undergone testing for immunogenicity, including screening, titer, or neutralizing characterization, as applicable.	Section 6.6
Team decided to modify the definition of TEAE as any AE occurred during the TE period, which includes the time from the administration of study drug until the Week 24 visit (or the Day 169,	Section 6.4

if the Week 24 visit is unavailable) for Part A, and the Week 8 visit (or the Day 57, if the Week 8 visit is unavailable) for Part B, C, and D to ensure a consistent reporting period across study cohorts	
---	--

6.8.2. Modifications to the Approved Statistical Analysis Plan

Not Applicable. This is the first version of the SAP.

7. SUPPORTING DOCUMENTATION

Appendix 1: List of Abbreviations and Definitions of Terms

AE	adverse event
ALT	alanine transaminase
AST	aspartate transaminase
BMI	body mass index (kg/m ²)
CI	confidence interval
CLDQ-HBV	Chronic Liver Disease Questionnaire-Hepatitis B Virus
CPT	Child-Pugh-Turcotte
CRO	contract research organization
CTCAE	Common Terminology Criteria for Adverse Events
DMC	Data Monitoring Committee
DNA	deoxyribonucleic acid
ECG	electrocardiogram
eCRF	electronic case report form
ECI	Events of Clinical Interest
FAS	full analysis set
HBcrAg	hepatitis B core-related antigen
HBV	hepatitis B virus
HBeAb	hepatitis B e antibody
HBeAg	hepatitis B e antigen
HBsAb	hepatitis B surface antibody
HBsAg	hepatitis B surface antigen
HCC	hepatocellular carcinoma
HDV	hepatitis Delta virus
ICF	informed consent form
LOD	limit of detection
LLOQ	lower limit of quantitation
ISR	injection site reaction
MAR	missing at random
Max	maximum value

MedDRA	Medical Dictionary for Regulatory Activities
MELD	Model for End Stage Liver Disease
METAVIR	Meta-Analysis of Histological Data in Viral Hepatitis
Min	minimum value
PD	pharmacodynamic/pharmacodynamics
PK	pharmacokinetic/pharmacokinetics
PR	PR interval is measured from the beginning of the P wave to the beginning of the QRS complex
PT	preferred term
QRS	Q, R, and S-wave define the QRS-complex in an ECG
QT	QT interval represents the duration of ventricular depolarization and subsequent repolarization; it is measured from the beginning of the QRS complex to the end of the T wave
QTc	QT interval corrected for heart rate
RNA	ribonucleic acid
SAE	serious adverse event
SAP	statistical analysis plan
SC	subcutaneous
SD	standard deviation
SOC	system organ class
T(N)D	target (not) detected
TEAE	treatment-emergent adverse event
ULN	upper limit of normal
WHODD	World Health Organization Drug Dictionary
WPAI - GH	Work Productivity and Activity Impairment Questionnaire – General Health

Appendix 2: Analysis Visit Windows for Safety, Efficacy, and Immunogenicity Assessment

Table 7-1 Analysis Visit Windows for Safety and Antiviral Assessments			
Assessment	Analysis Visit¹	Target Study Day	Analysis Visit Window (in study days)^{2, 3, 4, 5}
Part A: 
 Serum Chemistry Liver function tests Hematology Vital signs 	Day 1 (Baseline)	1	≤1 Pre-dose/post-dose
	Day 2	2	[1, 2]
	Day 4	4	(2, 6]
	Week 1	8	(6, 11]
	Week 2	15	(11, 22]
	Week 4	29	(22, 43]
	Week 8	57	(43, 71]
	Week 12	85	(71, 106]
	Week 18	127	(106, 148]
Week 24	169	(148, ≥176]	
Part A: 
 Local tolerability 	Day 1 (Baseline)	1	≤1 Pre-dose
	Day 2	2	[1, 2]
	Day 4	4	(2, 6]
	Week 1	8	(6, ≥176]
Part A: 
 Immunogenicity 	Day 1 (Baseline)	1	≤1 Pre-dose
	Week 2	15	[1, 22]
	Week 4	29	(22, 43]
	Week 8	57	(43, 71]
	Week 12	85	(71, 106]
	Week 18	127	(106, 148]
Week 24	169	(148, ≥176]	
Part A: 
 Pregnancy test 	Day 1 (Baseline)	1	≤1 Pre-dose
	Week 4	29	[1, 43]
	Week 8	57	(43, 71]
	Week 12	85	(71, 106]
	Week 18	127	(106, 148]
	Week 24	169	(148, ≥176]
Part B, C, and D: 
 Serum Chemistry Liver function tests Hematology Coagulation Vital signs 	Day 1 (Baseline)	1	≤1 Pre-dose/post-dose
	Day 2	2	[1, 2]
	Day 4	4	(2, 6]
	Week 1	8	(6, 11]
	Week 2	15	(11, 22]
	Week 4	29	(22, 43]
	Week 8	57	(43, min(≥64, Ext FU Day 1)]
Part B, C, and D: 
 HBsAg HBV DNA (Part D) 	Day 1 (Baseline)	1	≤1 Pre-dose
	Day 2	2	[1, 2]
	Day 4	4	(2, 6]
	Week 1	8	(6, 9]
	Day 11	11	(9, 13]
	Week 2	15	(13, 22]
	Week 4	29	(22, 43]
	Week 8	57	(43, min(≥64, Ext FU Day 1)]

Table 7-1 Analysis Visit Windows for Safety and Antiviral Assessments			
Assessment	Analysis Visit¹	Target Study Day	Analysis Visit Window (in study days)^{2, 3, 4, 5}
Part B, C, and D: • Anti-HBs • HBV DNA (Part B and C)	Screening (Baseline) Week 1 Week 2 Week 4 Week 8	<1 8 15 29 57	<1 Pre-dose [1, 11] (11, 22] (22, 43] (43, min(≥64, Ext FU Day 1)]
Part B, C, and D: • HBeAg • HBV RNA • HBcrAg • Pregnancy test	Day 1 (Baseline) Week 4 Week 8	1 29 57	≤1 Pre-dose [1, 43] (43, min(≥64, Ext FU Day 1)]
Part B, C, and D: • Anti-HBe	Day 1 (Baseline) Week 8	1 57	≤1 Pre-dose [1, min(≥64, Ext FU Day 1)]
Part B, C, and D: • Immunogenicity	Day 1 (Baseline) Week 2 Week 4 Week 8	1 15 29 57	≤1 Pre-dose [1, 22] (22, 43] (43, min(≥64, Ext FU Day 1)]
Part B, C, and D: • Urinalysis	Day 1 (Baseline) Week 1 Week 2	1 8 15	≤1 Pre-dose [1, 11] (11, min(≥64, Ext FU Day 1)]
Part B, C, and D: • Local tolerability	Day 1 (Baseline) Day 2 Day 4 Week 1	1 2 4 8	≤1 Pre-dose [1, 3] (3, 6] (6, min(≥64, Ext FU Day 1)]
Part B, C, and D: • Physical examination	Screening (Baseline) Day 4 Week 8	<1 4 57	<1 Pre-dose [1, 30] (30, min(≥64, Ext FU Day 1)]
CCI			
Extended Follow-Up Period (Part B, C, and D)			
• Pregnancy test • Liver function test • Serum chemistry • Immunogenicity • HBsAg and Anti-HBS • HBV DNA (Part D)	Ext Week 12 Ext Week 16 Ext Week 24 Ext Week 32 Ext Week 40	85 113 169 225 281	(Ext FU Day 1, 99] (99, 141] (141, 197] (197, 253] (253, ≥288]

Table 7-1 Analysis Visit Windows for Safety and Antiviral Assessments			
Assessment	Analysis Visit¹	Target Study Day	Analysis Visit Window (in study days)^{2, 3, 4, 5}
Part B, C, and D: 
 • HBV RNA • HBcrAg 	Ext Week 12 Ext Week 24 Ext Week 32 Ext Week 40	85 169 225 281	(Ext FU Day 1, 113] (113, 197] (197, 253] (253, ≥288]
CCI			
Part B, C, and D: 
 • HBeAg and Anti-HBe 	Ext Week 40	281	(Ext FU Day 1, ≥288]
Notes: 
¹ Visit name for analysis purpose is used to report data in tables and figures.
 
² The analysis visit windows will be applied using the following rules for both scheduled and unscheduled visits:
 
 a. If no numerical measurement is available within a visit window, the measurement will be considered missing for the visit. b. If there is more than 1 numerical measurement available within a visit window, use the following rules: 
 i. If the scheduled visit measurement will be used if it is available ii. If not, the unscheduled visit measurement closest to the target day will be used; or iii. If there are multiple unscheduled visit measurements with the same distance from the target day, the latest measurement will be used. 
³ For an assessment, e.g., laboratory, ECG and vital sign measurement collected on the date of first dose of study drug, if it cannot be determined whether the measurement is before or after the first dose:
 
 a. Scheduled measurement will be treated as pre-dose observation. b. Unscheduled measurement will be treated as post-dose observation. 
⁴ For vital signs, Day 1 will be included in the Day 1 visit window to account for the post-dose assessments on Day 1, .
 
⁵ PK analysis window will follow the protocol-defined assessment visit window.
			

